1 PROTOCOL SUMMARY

1.1 SYNOPSIS

Title:	Team-Based Connected Health to Improve Clinical Outcomes and Access in Atopic Dermatitis
Study Description:	This is a pragmatic, randomized, controlled, equivalency trial. This 12- month trial will evaluate the impact of an online, team-based connected health (TCH) model for management of atopic dermatitis (AD) as compared to in-person care. 300 patients will be randomly assigned to the online TCH model or the in-person control arm stratified by two factors: age (<18 years vs. 18+ years) and study site. This pragmatic, randomized trial will compare AD disease severity (Aim 1), quality-of-life and access-to- care measures (Aim 2), and costs (Aim 3) between the two models.
Objectives:	The primary goal of the protocol is to evaluate whether an online, team- based connected (TCH) health model results in equivalent improvements in disease severity and quality of life, provides better access to specialist care, and is cost-saving compared to usual in-person care for AD management. We will perform a pragmatic randomized equivalency trial to compare the online, TCH model versus in-person care. The specific aims of the study are as follows:
	Primary Objective (Aim 1) : Compare differences in AD severity, as measured by the Eczema Area and Severity Index (EASI), Patient-Oriented Eczema Measure (POEM), and validated Investigator Global Assessment (vIGA), between patients randomized to Team-Based Connected Health and in-person care in a 12-month pragmatic, randomized equivalency trial.

Endpoints:	Secondary Objectives (Aim 2): Compare differences in quality of life as measured by dermatology-specific instruments (Dermatology Life Quality Index / Children's Dermatology Life Quality Index) and a generic instrument (European Quality of Life-5 Dimensions) between patients randomized to Team-Based Connected Health and in-person care. Furthermore, we will compare differences in access-to-care measures such as transportation and time needed for evaluation between patients randomized to Team-Based Connected Health and in-person care. Secondary Objectives (Aim 3): Compare differences in healthcare costs from a societal perspective between Team-Based Connected Health and in-person care through cost-minimization analysis. The primary and secondary endpoints are as follows: Primary Endpoint :			
	• Change in EASI from baseline averaged across 12 months.			
	 Secondary Endpoints: Change in vIGA from baseline averaged across 12 months Change in POEM from baseline averaged across 12 months Change in DLQI and CDLQI from baseline averaged across 12 months Change in EQ-5D-5L and EQ-5D-Y from baseline averaged across 12 months Patient reported access-to-care outcomes, including transportation and time needed for evaluation Healthcare utilization and costs from a societal perspective 			
Study Population:	The study population consists of children and adults (age 1 year and older) with atopic dermatitis (AD). We plan to enroll 300 patients representing the full spectrum of AD disease severity in southern California.			
Description of Sites/Facilities Enrolling Participants:	Ambulatory clinics associated with Keck Medicine of University of Southern California and LAC+USC Medical Centers will participate in enrolling participants.			
Description of Study Intervention:	The Team-Based Connected Health (TCH) model enables structured online interactions among patients, primary care providers (PCPs), and dermatologists. The goal of TCH is to provide patients and PCPs with high-quality online communication with specialists that would otherwise occur in person.			
Study Duration: Participant Duration:	60 months 12 months			

1.2 SCHEMA

1.3 SCHEDULE OF ACTIVITIES (SOA)

Procedures/Assessments	Month 0 / Baseline	Month 3	Month 6	Month 9	Month 12
	+ 28 days	-7 days, +21 days	-7 days, +21 days	-7 days, +21 days	7 days, +28 days
Informed Consent	Х				
Randomization	Х				
Patient or parent/legal guardian					
training on utilization of the	Х				
teledermatology platform					
Baseline Demographics and Medical	x				
History	~				
Atopic Dermatitis Severity Assessments		1	1	1	r
EASI	Х	Х	Х	Х	Х
vIGA	Х	Х	Х	Х	Х
POEM	Х	Х	Х	Х	Х
Quality of Life Assessments			•		
DLQI / CDLQI	Х	Х	Х	Х	Х
EQ-5D-5L / EQ-5D-Y	Х	Х	Х	Х	Х
Access to Care					
Access to Care (Baseline)	Х				
Access to Care (Follow-up)	х	Х	х	х	Х
Healthcare Costs Assessments					
Cornell Services Index	х				Х
Safety Assessments					
Adverse Event Collection Form	Х	Х	Х	Х	Х

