5.4.2 RETENTION PLAN

Prior to study initiation, we will conduct pre-trial retention training for the study staff. Prior to enrollment, the study staff will communicate with eligible patients regarding the importance of completing all outcome assessments. We will emphasize the importance of full participation during screening, enrollment, and throughout the trial.

It is important to note that, for online and in-person visits between the provider and patients, these visits occur at an individualized frequency based on medical necessity. However, the collection of outcome assessments (disease-severity, quality-of-life endpoints, and selected access-to-care measures) occurs at a quarterly basis for all participants.

All subjects will be reminded via email, text, or telephone to submit their quarterly outcome assessments beginning 7 days prior to the due date. If a subject fails to submit the quarterly outcome assessments within 2 days of the due date, the subject will be contacted using telephone and/or electronic methods to remind them to submit the assessments. The study staff will also discuss with the participant strategies to improve adherence with the study requirements. If the participant cannot be contacted after at least five attempts, a certified return receipt letter will be sent to encourage continuation in the trial.

If a participant fails to complete a quarterly assessment within 21 days of the due date, the study staff will make at least five attempts to contact (at least three telephone calls, two emails, and, if necessary, a certified return receipt letter to the participant's last known mailing address or local equivalent method). These contact attempts will be documented in the participant's study file.

If a participant wishes to withdraw from the study, the study coordinators will attempt to collect the Month 12 visit data as well as detailed data on the reasons for the discontinuation from the study. The study coordinators are encouraged to share their ideas and experiences to promote participant retention via regular communication during staff meetings.

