9.3 STATISTICAL ANALYSES

9.3.1 GENERAL APPROACH

For this pragmatic, randomized trial, we will compare patients randomized to the online, team-based connected health (TCH) versus patients receiving in-person care across one year. The overall analytical strategy is to use linear mixed or generalized estimating equations, depending on the outcome variable, to account for repeated measures within patients. Random effects for patients will be included in the model so that the estimates of any patient-level variables will be appropriately calculated. Additionally, we will adjust *a priori* for the randomization stratification factors site and age group (<18 years, and 18+ years) in all models. While we do not anticipate a site-level main effect, random effects for site will be included in the model in case there are factors common to patients within a site that affect the outcome.

For comparison of AD disease severity (Aim 1) and quality of life (Aim 2), we will test an equivalence hypothesis between the interventions using longitudinal linear mixed effects modeling; this allows for the estimation of intra-individual variance. Using this same technique, we will test the hypothesis of improved access to specialist care (Aim 2) and cost-saving (Aim 3) with the TCH model compared to the in- person model.

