The hypothesis for access-to-care measures is that TCH provides *superior* access to specialist care than in- person model. For these analyses, access-to-care measures include transportation and time needed for evaluation.

Linear regression models will be used to test whether there is a difference between the groups.

Analysis of Costs (Aim 3)

Cost analysis in healthcare research is essential for evaluating the financial impact of different treatment models on both patients and healthcare systems.²⁶⁻²⁷ For this aim, out-of-pocket (OOP) costs represent a significant factor in determining the feasibility and accessibility of team-based connected health (TCH) compared to traditional in-person care for atopic dermatitis (AD). By analyzing OOP expenditures, this study will provide insights into whether TCH offers a cost-effective alternative while maintaining equivalent clinical outcomes.³¹⁻³⁸

Healthcare utilization will be analyzed using the Cornell Services Index (CSI), which quantifies visit frequency, duration, and associated costs for medical, psychological, and professional consultations.³⁰ CSI data will be collected at baseline and again at 12 months, with ITT analysis requiring baseline values to be duplicated for patients missing follow-up data. Visit counts for different service categories will be analyzed through linear models, with treatment status as the primary predictor. Mean visit duration per patient and visit type will be compared across the two groups using Welch's two-sample t-tests and linear regression models incorporating total visit count as a covariate. The impact of TCH on visit duration will be further assessed using analysis of variance (ANOVA) models to determine potential treatment group differences. Additionally, sub-analyses will be conducted to explore whether utilization patterns differ by age or baseline disease severity. Given the pragmatic design of the study, an emphasis will be placed on real-world applicability, ensuring that findings account for the variability seen in routine clinical settings.

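### Access to care (Aim 2): sections 9.3.1 and 9.3.3 name different models, the Month 0 record has no defined role, and adjusting for it would gain precision at no data cost

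*Combined protocol and SAP*

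**What the plan says.** **Collection.** Section 1.3 has two access rows. "Access to Care (Baseline" is marked at Month 0 only. "Access to Care (Follow-up" is marked at all five time points, including the column headed "Month 0 / Baseline". That column also holds consent, randomization and platform training, with a window of + 28 days. Section 5.4.2 confirms repeated collection: "selected access-to-care measures) occurs at a quarterly basis for all participants".

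**Endpoint.** The Synopsis lists "Patient reported access-to-care outcomes, including transportation and time needed for evaluation". The other repeated secondary endpoints (vIGA, POEM, DLQI/CDLQI, EQ-5D) are each defined as a change from baseline averaged over 12 months. Access is not, and no visit set is attached to it.

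**Analysis.** Section 9.3.3 states: "The hypothesis for access-to-care measures is that TCH provides *superior* access to specialist care". The method follows in one sentence: "Linear regression models will be used to test whether there is a difference between the groups". It names no visits, no way of combining repeated records and no baseline covariate. Section 9.3.1, after describing longitudinal mixed modeling for severity and quality of life, says: "Using this same technique, we will test the hypothesis of improved access to specialist care (Aim 2". It fixes site and age group as covariates in all models.

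**Baseline coding.** Section 9.3.2 codes time as 0 for baseline and 1 for all follow-up visits, with a group-by-time term, for EASI. Section 9.3.3 carries that approach over to quality of life but not expressly to access.

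**The concern.** Two analysts could each follow the plan and run different access analyses: a regression as in section 9.3.3, or a mixed model as in section 9.3.1. Neither section says what the follow-up form at Month 0 is for. It could be a baseline value, one of five outcome records, or unused.

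The choice matters because access is a superiority claim and better access is part of the trial's stated primary goal. If baseline access is collected but left out of the model, the standard error is larger than it need be. If the Month 0 record entered as an outcome, it could pull the estimated benefit toward zero.

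**Working it through.** The plan gives no effect size, SD, correlation or power for access, so there is no access figure of its own to reproduce. The check compares the analyses that the text permits.

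**Assumptions (none is in the documents).** Each access record has SD 1. All pairs of records on one patient have the same correlation ρ, tried at 0.3, 0.5 and 0.7. The treatment effect is constant over Months 3-12 and zero at Month 0. The test is two-sided at 0.05.

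**Variance per patient.** Multiplying by 2/n per arm gives the variance of the group contrast, and n cancels in every ratio.

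- Mean of Months 3-12, unadjusted: V4 = (1 + 3ρ)/4
- Same mean, Month 0 access as covariate: VA = V4 − ρ², since the covariance of Month 0 with the mean is ρ
- Group-by-time change estimate with separate baseline means per arm (the section 9.3.2 coding): VD = V4 + 1 − 2ρ
- Mean of all five records: V5 = (1 + 4ρ)/5

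| ρ | V4 | VA | VD | V5 | VA/V4 | SE ratio √(VA/V4) |
|---|---|---|---|---|---|---|
| 0.3 | 0.475 | 0.385 | 0.875 | 0.440 | 0.81 | 0.90 |
| 0.5 | 0.625 | 0.375 | 0.625 | 0.600 | 0.60 | 0.77 |
| 0.7 | 0.775 | 0.285 | 0.375 | 0.760 | 0.37 | 0.61 |

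**Power.** Take an effect with 80% power on the unadjusted Months 3-12 mean, so its expected z is 1.96 + 0.84 = 2.80. Power under another analysis is Φ(2.80 × k × √(V4/V) − 1.96), where V is that analysis's variance and k is the share of the effect it recovers.

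| Analysis | k | ρ = 0.3 | ρ = 0.5 | ρ = 0.7 |
|---|---|---|---|---|
| Months 3-12, unadjusted | 1 | 80% | 80% | 80% |
| Months 3-12, Month 0 covariate | 1 | 88% | 95% | 99.6% |
| Group-by-time change estimate | 1 | 54% | 80% | 98% |
| All five records pooled | 0.8 | 64% | 63% | 62% |

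**The pooled row.** One record with no effect averaged with four carrying effect δ gives (0 + 4δ)/5 = 0.8δ, a 20% reduction. A simulation at ρ = 0.5 also gave a ratio of 0.80. This row shows what would follow if Month 0 were treated as an outcome; it does not describe a stated plan.

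**Reading the table.** The covariate analysis is the most precise at every ρ tried. The change estimate is not diluted, but it is less precise than the unadjusted mean at ρ = 0.3, equal to it at 0.5 and better at 0.7.

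**The case against.** The strongest reply is section 9.3.1. If access is analysed with the mixed model and the section 9.3.2 coding, Month 0 is the reference level, the group-by-time estimate is not diluted and the Month 0 record is used. That stands, so a reader may not conclude that the Month 0 value is used nowhere in the plan. The reply does not settle the matter. Section 9.3.3 is the endpoint-specific text and names a different model, the coding is not expressly extended to access, and the change estimate is still less precise than the covariate analysis.

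Other stronger readings also fail:

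- **That the plan dilutes the access effect by 20%.** No section says that Month 0 is pooled as an outcome.
- **That the Month 0 form necessarily precedes care under the assigned model.** The column includes randomization and training and has a + 28 day window, so a form might be completed after a first visit. The 20% is therefore an upper figure under a constant effect.
- **That the Month 0 mark is a mistake to be deleted.** The access forms are not in the documents. Using the follow-up form at Month 0 may be how the same items are obtained at baseline.

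It is also fair to say that an unadjusted randomized comparison is valid, that site and age group are already planned covariates, and that a measure of travel and time need not be defined as a change from baseline. The correlation could be low, or could differ between arms because online care itself alters travel. These points limit the finding to precision and clarity; they give no reason to leave the model unspecified.

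**Conclusion.** The point holds as a free improvement. The documents establish three things: a follow-up access form is scheduled at Month 0, sections 9.3.1 and 9.3.3 name different models for access, and neither defines the outcome visits or the role of baseline access. Under the section 9.3.3 regression this costs precision and does not bias the randomized contrast.

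The size rests on an assumed equal between-record correlation. At 0.3, 0.5 and 0.7, adjustment reduces the standard error of the Months 3-12 comparison by about 10%, 23% and 39% (1 minus 0.90, 0.77 and 0.61). If baseline and follow-up access were uncorrelated there would be no gain. Dilution is a conditional risk that a clear definition removes; the documents do not support stating it as an expected result.

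**What to change.** 1. Keep the Month 0 access record and designate it as baseline. Remove the mark from the follow-up row only if the baseline form is confirmed to hold the same travel and time items.
2. State that the Month 0 record is to be completed before the first visit under the assigned model. A later record could already reflect the intervention, and adjusting for it could remove part of the effect.
3. Define the access outcome as Months 3-12 and say how the repeated records are combined.
4. Name one model for access, with the Month 0 value of the same measure as a covariate alongside the site and age-group terms already planned.
5. Amend sections 9.3.1 and 9.3.3 so that both describe that model.

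The cost is text edits to the schedule note and the statistical section. No new data, visits or participants are needed.

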2 INTRODUCTION

2.1 STUDY RATIONALE

Chronic skin diseases are associated with markedly decreased quality of life and financial consequences.¹⁻² In the U.S., access to dermatologists remains a significant challenge, especially for those in underserved or rural communities.³⁻⁷ Even after an initial evaluation by a dermatologist, many patients have difficulties maintaining regular access to dermatologists for follow-up care. Consequently, many patients experience worse clinical outcomes and reduced quality of life.⁸

With the maturation in communication technology to facilitate healthcare, now is the critical time to determine how technology-enabled healthcare delivery models impact patient outcomes, access, and costs in the real world.

We will evaluate an online, team-based connected health (TCH) model that enables structured asynchronous online interactions among patients, primary care providers (PCPs), and dermatologists. The goal of TCH is to provide patients and PCPs with high-quality online communication with specialists that would otherwise occur in person. TCH leverages innovative health services model and technology to bring expert care to patients and PCPs in a location-independent and asynchronous manner.

Atopic dermatitis (AD) is the ideal disease model to evaluate TCH because it is common, chronic, and can inflict substantial morbidity if not managed effectively.⁹⁻¹¹ To address skin inflammation, itch, and psychosocial consequences, PCPs and dermatologists need to adopt a team-based approach to effectively manage all aspects of the disease.

2.2 RISK / BENEFIT ASSESSMENT

2.2.1 KNOWN POTENTIAL RISKS

As with all electronic health information exchange and record platforms, potential risks include loss of confidentiality. Our research team has extensive experience protecting privacy and maintaining confidentiality of our patients' personal information on telemedicine platforms. The teledermatology platform is secure and HIPPA compliant, and it has been used for online telemedicine visits and for telemedicine studies. We deem the probability of experiencing loss of confidentiality of protected health information low. Specific mitigation strategies to ensure data security and confidentiality are discussed below in the section 10.1.3 "Confidentiality and Privacy".

Because we are recruiting patients with AD across the spectrum of disease severity, potential risks remain with either arm of the study with regards to adverse events related to AD or its associated treatments. Because the study is pragmatic in design, it enables in-person or online visits at frequencies that are individualized and deemed medically necessary by the provider. Thus, providers and patients in both arms can follow up at frequencies that are necessary to manage AD and any treatment-related adverse events. Furthermore, the patients randomized to the online arm could seek in-person care if the patient or the provider deem that online care is insufficient to address a problem. Thus, we deem the probability of experiencing untoward events by the study participants not higher than what would otherwise be expected via routine care.

2.2.2 KNOWN POTENTIAL BENEFITS

The TCH model offers several distinctive benefits. The model offers multiple ways for both patients and PCPs to access dermatologists online asynchronously that are responsive to real-world needs. The patients can also upload clinical images and history online and obtain asynchronous evaluation and recommendations from the dermatologists. PCPs can upload patient's photos and history online and access dermatologists asynchronously for consultations or to request a dermatologist to assume care of a patient's atopic dermatitis.

Overall, the TCH model not only increases patient and provider engagement; it also provides comprehensive specialist support to both PCPs and patients. TCH eliminates the need for patients to find a local healthcare facility with telemedicine capabilities to engage dermatologists via telemedicine. After careful consideration of the benefits and risks associated with the study, we deem the benefit-risk assessment to be acceptable to research participants. The accessibility of quality and timely specialist care for atopic dermatitis patients outweighs the potential adverse risks associated with the study.

2.2.3 ASSESSMENT OF POTENTIAL RISKS AND BENEFITS

Evidence supports accuracy and reliability of diagnosis by asynchronous teledermatology. Furthermore, multiple studies have demonstrated concordance in management plans between care delivered through asynchronous teledermatology versus in person. However, potential risks remain with either arm of the study with regards to adverse events related to AD exacerbation or adverse events arising from AD treatment. Because the study is pragmatic in design, it enables in-person or online visits at frequencies that are individualized and deemed medically necessary by the provider. Thus, providers and patients in both arms can follow up at frequencies that are necessary to manage AD and any treatment-related adverse events. Thus, we deem the probability of experiencing untoward events beyond what would otherwise be expected via routine care for this population to be low.

Protection against Adverse Events during Management of Atopic Dermatitis

To mitigate risks of adverse events related to AD or the treatment, the PI and the study staff will continuously monitor patients for adverse events. Patients can report adverse events using two methods: (1) using the "Adverse Event Collection Form", which is captured at quarterly intervals, or (2) reporting AEs spontaneously to the study at any time 24/7. The study team or the patient's provider will address adverse events as they occur.

3 OBJECTIVES AND ENDPOINTS

OBJECTIVES	ENDPOINTS	JUSTIFICATION FOR ENDPOINTS
Primary		
Aim 1: Compare differences in atopic dermatitis disease severity, as measured by Eczema Area and Severity Index (EASI), and validated Investigator Global Assessment (vIGA), and Patient-Oriented Eczema Measure (POEM) between patients randomized to TCH and in-person care in a 12-month pragmatic, randomized equivalency trial.	 The primary endpoint of the study is the mean improvement from baseline in EASI averaged across 12 months. The mean improvement in EASI is defined as the difference in EASI between baseline and the average of the follow-up visits (months 3-12). Secondary endpoints for Aim 1 include: Change in vIGA from baseline averaged across 12 months Change in POEM from baseline averaged across 12 months 	EASI is a validated, granular assessment of AD patient disease severity. It is commonly used in clinical trials, including trials for therapeutic approvals. By using EASI, we will be able to compare the results of this study with other studies in AD patients. The 5-point IGA is a valid measure of disease severity and meets the need for a clinically meaningful measure for atopic dermatitis. POEM is a validated patient-reported outcome used to

SecondaryAim 2: Compare differences in quality of life as measured by dermatology-specific instruments (Dermatology Life Quality Index (DLQI)/ Children's Dermatology Life Quality Index (CDQI)) and a generic preference-based instrument (European Quality of Life-5 Dimensions), between patients randomized to TCH and in-person care.Compare differences in access-to- care measures such as transportation and time needed for evaluation between patients randomized to TCH and in-person care.	 The secondary endpoints for Aim 2 include: Change in DLQI or CDLQI from baseline averaged across 12 months between the in-person and online groups Change in EQ-5D-5L or EQ-5D-Y from baseline averaged across 12 months between the in-person and online groups. Transportation and time needed for evaluation between the in-person and online groups. 	monitor AD severity that focuses on the illness as experienced by the patient. The DLQI and the CDLQI are validated, 10- question questionnaires that can be used to assess dermatology- specific quality of life in adults and children with atopic dermatitis. EQ-5D-5L and EQ-5D-Y are validated measures of health status. The EQ- 5D-5L and EQ-5D-Y provide a single index value that can be used for QoL and economic evaluations. Transportation and time needed for evaluation are measures of access.
Secondary		
Aim 3: Compare differences in healthcare costs between TCH and in-person care.	The secondary endpoints for Aim 3 are:Healthcare utilizationHealthcare costs	The Cornell Services Index is a validated method to assess health service use. The measure provides a reliable snapshot of service use patterns across types, providers, and sites of service among adults who seek medical care.

